### **10.1.2.21. CT/PET**

CT/PET was used for a single adult patient once in place of a MRI/PET. CT/PET would be used in up to two more adult patients in place of MRI/PET if MRI/PET is unavailable. This would be done for the scientific integrity of the protocol in the setting that a MRI/PET could not be obtained. For these individuals their total research radiation dose would be 4.01 rem, which is 0.17 more than they would receive had they had a MRI/PET. This is still below the recommended research threshold of 5 rem/year in adult patients.

Using the PET component of the CT/PET will obtain the similar information as to the MRI/PET (Section 10.1.2.5). The PET component of the scan will allow us to determine if a calcinosis lesion is active or not. By observing lesions with PET before treatment, we will be able to determine if certain metabolic levels of lesions are more prone to responding to therapy. This may allow patients to receive a PET scan to better determine their ability to respond. Looking at metabolic activity of the calcinosis lesions will also allow us to determine if there is a change in activity with treatment. An increase in metabolic activity in calcinosis lesions post treatment may represent an early sign of calcinosis reformation or resolution. By monitoring for this change in metabolic activity, we may be able to tell patients where they are most likely to have calcinosis reoccurrence and those areas could be targeted for additional therapy. We have also seen differences in the longevity of patients' response to therapy and feel PET imaging can help give insight into determining which patients are likely to have a sustained response and which ones will not. The direct benefit involves the ability to better understand the activity of a patient's disease, which can help guide therapy. It can be

**Abbreviated Title:** Sodium Thiosulfate (STIC)

**Version Date:** July 07, 2023

difficult on traditional MRI to distinguish active disease from damage in an area with prior damage and adding the PET scan component improves the ability to do this.

### **10.1.2.22. Summary/Classification of Risk: Benefit for the Study as a Whole**

All participants and/or their parents will be fully informed of all pertinent study procedures, volunteer responsibilities, and the risks and benefits of participating in this protocol by informed consent procedures. The study will also obtain pediatric assent whenever possible, dependent on participant maturity, to ensure proper understanding.

Adults and children participating in this study may receive direct benefit for their calcinosis from treatment with the product under investigation (sodium thiosulfate). The procedures included in this study are widely used. The CT scan and MRI/PET aspects of this study represent an increase over minimal risk with the potential for direct benefit. The other procedures in this study pose a minor increase over minimal risk to the participant. The participants in this study will receive a therapeutic compound at an unapproved dose for an unapproved indication, thus this study as a whole is considered to pose more than minimal risk. However, since there are currently no known alternative therapeutic options for these patients to effectively improve their calcinosis, the potential risk is reasonable in relation to the potential clinical benefit they may derive from participating in the study.

The study is likely to yield generalizable knowledge about the impact of sodium thiosulfate on calcinosis associated with dermatomyositis, the safety of IV sodium thiosulfate, and could enhance our understanding of the pathogenesis of calcinosis associated with dermatomyositis.

This study is classified as Category 2 research for children, because it involves greater than minimal risk but presents the prospect of direct benefit to the individual child.

## **11. Protection of Participants' Privacy and Confidentiality**

The investigator will ensure the protection of the participant's privacy and the confidentiality of identifiable data collected during research in accordance with NIH HRPP Policy 107 - *Privacy and Confidentiality*. Safeguards of privacy will include to the extent possible: providing private areas for obtaining consent, collecting information, and conducting examinations and research procedures; limiting the presence of research staff or others present during procedures; limiting information collected to that pertaining to the stated research objectives; and limiting information collected about those who are not the subject of research (e.g., family members or other potential participants). Procedures that will be used to maintain the confidentiality of data and medical records are described in Section 17.

## **12. Study Agents/Interventions**

This section describes the study treatment (i.e., administration of sodium thiosulfate); all other study interventions are described in Section 4.1.

**Abbreviated Title:** Sodium Thiosulfate (STIC)

**Version Date:** July 07, 2023

## **12.1. Supply and Preparation of Sodium Thiosulfate**

Sodium thiosulfate will be supplied by Hope Pharmaceuticals (Scottsdale, Arizona, USA) in 50-mL vials containing 12.5 grams of sodium thiosulfate at a concentration of 250 mg/mL. This solution has an osmolarity of 2,250 mOsm/L. Study drug will be prepared as 12.5 grams of sodium thiosulfate in 450 mL of D5W for an osmolality of 538 mOsm/L. In patients who have problems with the volume of fluid or if there is a shortage of D5W then sodium thiosulfate can also be prepared at concentrations of 27.8 mg/mL to 71.4 mg/ml in D5W for osmolalities of 538 mOsm/L to 899mOsm/L. All medication will be received by the NIH pharmacy. Stability experiments have been run and the medication is stable at these concentrations for at least 24 hours.

## **12.2. Intravenous Administration of Sodium Thiosulfate**

Sodium thiosulfate will be administered intravenously to participants at a dose of 16 g/m^2 per each infusion. The infusion will be administered over a period of approximately 3 hours; for patients experiencing nausea, the rate can be slowed up to half of the normal rate. In addition, for patients where the drug volume is felt to be unsafe to give over a 3 hour period the infusion time can be increased to up to 6 hours.

After the infusion, adult participants who can tolerate it will receive up to 1 L of normal saline to promote urinary excretion of calcium. Pediatric patients who can tolerate it will receive 5-10 cc/kg to a maximum of 1 L of IV normal saline post sodium thiosulfate infusion. Ability to tolerate additional infusion will be based on clinical exam at time of infusion, the patient's medical history, tolerance of prior infusions, and laboratory results.

During the treatment period, infusions will be administered 3 times weekly for 10 weeks.

Sodium thiosulfate will always be administered under the supervision of a medical practitioner who is licensed to give intravenous therapy.

If new osteoporotic fractures develop during treatment participants will have study drugged stopped, but will continue with all assessments. If a patient develops a fracture prior to starting study drug, but after enrollment they may return in 1 year or longer period of time to have a second -10 visit and then continue with the study based on that date. During the 1 year or longer weight the patient would be allowed to start a bisphosphonate.

Patients have been reported to have nausea with infusions of sodium thiosulfate. Nausea may be treated by a physician, including pretreatment if needed, with each infusion with anti-emetics, such as Zofran.

As described above, IV normal saline may be administered following each infusion, and participants will be encouraged to maintain oral hydration status between infusions. It is thought that increasing patient hydration will allow more of the calcium thiosulfate to be excreted. Patients experiencing fevers, chills or hypotension will be pre-medicated with Tylenol and Benadryl. Patients experiencing high serum phosphate levels during the treatment period may receive sevelamer.

*Abbreviated Title:* Sodium Thiosulfate (STIC)

*Version Date:* July 07, 2023

### **12.3. Justification for Selection of Dose and Frequency of Sodium Thiosulfate**

We have chosen a dose of 16 g/m^2 for this study. Based on the previously done human studies and existing animal data this dose should be able to be administered without serious adverse events. Based on cases we have accumulated this appears to be a dose where patients tend to respond, with poor response to low dose treatment. Based on the case reports we have accumulated this appears to be the minimal dose with a significant beneficial effect. With the published side effect data, there is also a trend towards greater electrolyte abnormalities at larger doses so we tried to keep dosing below 20 g/m^2.

We would like to maximize drug frequency in order to minimize the time it takes patients to get all of their infusions. In a study of sodium thiosulfate for cisplatin toxicity patients received medication 3 times a week with minimal side effects except for nausea (NCT00716976 unpublished data). They noted that some electrolyte abnormalities in these patients could persist for 24 hours, but very rarely beyond that. Based on this there is a concern that infusions more frequent than three times a week will not give patients enough time to completely correct any transient hypernatremia or hypocalcemia and thus they could accumulate a larger change eventually becoming clinically dangerous. In those patients who had electrolyte abnormalities beyond 24 hours it was often elevated phosphorus. We will monitor patients for this and in those with elevated phosphorus we will initiate sevelamer to reduce their phosphorus. In the cases, we have heard those patients who were on twice a week dosing tended to have stabilization of their calcinosis, but not improvement so we felt there was a need for at least three times a week infusions.

### **12.4. Acquisition and Accountability**

If any investigational product remains in the NIH Clinical Center Pharmacy after the last dose of sodium thiosulfate has been administered per protocol, the remaining investigational product will be disposed of according to the guidance in the Investigational Product Disposition SOP and Pharmacy's policy.

### **12.5. IND Information**

Sodium thiosulfate is not currently indicated for the treatment of calcinosis and thus an IND will be filed prior to the conduct of this study. NIEHS will serve as the sponsor for this IND. This study has received an IND of number 135039. The date of receipt by the FDA was April 13, 2017.

## **13. Adverse Event and Unanticipated Problem Reporting**

### **13.1. Definitions**

Adverse events, non-compliance both serious or continuing, protocol deviations both major and minor, as well as unanticipated problems will be reported to the IRB as defined and described by the NIH Office of Human Subjects Research Protection policy #801. In order to compare events across the length of the protocol we plan to continue to

**Abbreviated Title:** Sodium Thiosulfate (STIC)

**Version Date:** July 07, 2023

report to the FDA, DSMB, Clinical Director (CD), and Hope Pharmaceuticals according to the prior regulations and terminology as described below. If an event occurs that is reportable in a more expedited manner or at a higher level of reporting under NIH policy #801, then that policy's timelines will take priority. The following terms are defined as described in NIH HRPP SOP 16 ("Reporting Requirements for Unanticipated Problems, Adverse Events and Protocol Deviations"): Adverse Events (AE), Serious Adverse Event (SAE), Protocol Deviation (PD), serious, Unanticipated Problem (UP), and Unanticipated Adverse Device Effect (UADE).

All AEs occurring during the study, including those observed by or reported to the research team, will be recorded. The PI will ensure events are reported according to the requirements of NIH HRPP SOP 16.

In reference to the timings described below, the applicable institutional review board (IRB) for this protocol is the NIH Central IRB and the applicable Clinical Director (CD) for this protocol is the NIEHS CD.

### **13.2. Serious Events**

Reporting for *serious events* will be as follows:

- The PI will report serious UPs, serious PDs, and UADEs to the IRB and CD as soon as possible, but not more than 7 days after first learning of the event.
- The PI will report any SAEs immediately according to requirements of 21 CFR 312.64(b).
- All events will also be reported along the same time frame to Hope Pharmaceuticals.

### **13.3. Not Serious Events**

Reporting *not serious events* will be as follows:

- The PI will report all UPs that are not serious to the CD no more than 14 days after first learning of the event.
- The PI will report all PDs that are not serious no more than 14 days after first learning of the event.
- Non-serious protocol deviations will only be reported (within 14 days after the PI first learns of the event) if they represent a departure from NIH policies for the conduct of human subjects research, adversely affect the health care of the subject(s) or compromise the interpretation or integrity of the research. Non-serious protocol deviations that result from normal subject scheduling variations or technical issues associated with sampling that does not impact the health of the subject or the interpretation of the study data will not be reported.

By definition, all UADEs are "serious" and will be reported as described in Section 13.2.

### **13.4. Deaths**

All deaths that are possibly, probably or definitely related to the research will be reported to the IRB within 24 hours after the PI first learns of the event. The PI will report all

**Abbreviated Title:** Sodium Thiosulfate (STIC)

**Version Date:** July 07, 2023

deaths to the CD as soon as possible, but not more than 7 days after first learning of the event.

### **13.5. Reporting at Time of Continuing IRB Review**

At the time of continuing IRB review, the PI will provide the IRB an aggregated summary of all UPs, all PDs, all UADEs, and all AEs.

The following anticipated non-UP adverse events are expected to occur with high frequency, and they generally cause only minimal distress and no permanent damage:

We expect a high frequency of the risks and/or discomforts of phlebotomy, which are a common occurrence that generally causes only minimal distress and no permanent damage.

We expect a high frequency of the risks and/or discomforts of obtaining IV access, which are a common occurrence that generally causes only minimal distress and no permanent damage.

Variations in the amount of blood drawn, as the amount may be based upon clinical indication and the participant's weight and other recent blood testing completed.

However, the maximums of whole blood collected for research purposes in children will not exceed 5 mL/kg in a single day or 9.5 mL/kg in an eight-week period, and in adults will not exceed 10.5 mL/kg or 550 mL, whichever is smaller, over 8 weeks.

Due to blood draw limits based on size it may not be possible to draw all blood tests for a given day. In this situation, efforts will be made to draw those tests missed at the next available scientifically logical opportunity, but some blood tests may need to be skipped. A priority of blood draw is indicated in Appendix B where blood draws are listed in order of priority. Due to the commonality of this problem in smaller children, we will not plan to report these protocol deviations.

In some instances, there are errors with phlebotomy where not all blood work ordered is drawn. If this occurs we will attempt to draw those missed tests at the next available scientifically logical opportunity if for research purposes only, but they may be skipped. If they are needed for safety monitoring purposes they will be drawn immediately.

Some blood work must be done fasting and certain urine studies must be collected at specific points. As patients often accidentally eat and/or fail to properly collect their urine, we will not report samples missed due to these situations, and we will work to collect them at the next available scientifically logical opportunity, but some samples may be missed and this will not be reported as a protocol deviation.

Although some blood tests require the participant to be fasting, in the event that the participant is unable to fast, tests may occur in the non-fasting state and/or fasting labs will not be collected.

### **14. Data and Safety Monitoring**

The clinical and laboratory procedures used in this study represent a minor increase over minimal risk for study participants. However, repeat-dose IV administration of sodium thiosulfate is not approved in the US for any indication, and this drug is not approved for the treatment of calcinosis associated with dermatomyositis; therefore, we plan to utilize a Data and Safety Monitoring Board (DSMB), adverse event monitoring, and ongoing site monitoring.

**Abbreviated Title:** Sodium Thiosulfate (STIC)

**Version Date:** July 07, 2023

## **14.1. Use of Data and Safety Monitoring Board**

To further protect the rights and welfare of participants in this trial, which will enroll from a vulnerable population (i.e., children), and because safety information on the long-term use of sodium thiosulfate is limited, we plan to use a Data and Safety Monitoring Board for this study. The DSMB will have complete independence from the study team.

During the course of the study, the DSMB will review cumulative study data biannually to evaluate safety, efficacy, study conduct, and scientific validity and integrity of the trial. As part of this responsibility, DSMB members must be satisfied that the timeliness, completeness, and accuracy of the data submitted to them for review are sufficient for evaluation of the safety and welfare of study participants. The DSMB may also convene as needed if any safety issues arise that the Principal Investigator and/or NIEHS Clinical Director or designee would like the DSMB to address. DSMB member will receive all reports of serious adverse events within 48 hours of the occurrence. The DSMB will operate under a charter and its membership and charter will be approved by the NIEHS Clinical Director. The DSMB will report its written findings from each meeting to the NIEHS Clinical Director and the study PI.

The DSMB will consist of three members minimum. It will include at least one pediatric physician, one adult physician, and one individual with biostatistical experience. The members of the board should include individuals with expertise in auto-immune diseases and individuals familiar with managing calcinosis. The DSMB chair will have prior experience sitting on a DSMB.

The principal investigator will submit the written DSMB recommendations to the IRB upon receipt.

## **14.2. Subject Monitoring**

Tests used to monitor participant safety are described in Section 14.3 below.

Throughout the treatment period, inpatient participants will be monitored daily while in the clinical center and participants who elect to stay locally and come to the NIH for treatments will be monitored 3 times weekly. Additional visits occurring approximately 14 weeks and 52 weeks after the treatment period ends will allow for an assessment of any delayed safety or efficacy issues. Any new medical issues that arise during treatment will be addressed and managed.

Criteria for individual participant withdrawal from the treatment phase of the study include:

- Inability to comply with the requirements of the protocol (including inability to tolerate the sodium thiosulfate therapy)
- Breastfeeding or pregnancy detected prior to Week 10
- Serious adverse event necessitating discontinuation of the sodium thiosulfate therapy.
- Common Terminology Criteria for Adverse Events level 3 or greater event thought to be related to study drug, besides nausea, prior to week 10.
- Nausea that cannot be controlled by slowing rate of infusion and adding anti-emetic medications prior to week 10.

**Abbreviated Title:** Sodium Thiosulfate (STIC)

**Version Date:** July 07, 2023

- A new fracture prior to week 10. If a patient develops a fracture prior to week 0 if the patient would meet enrollment criteria in a year or greater time they may have a second -10 visit and continue from there with the normal study process.
- Patient request to withdraw from the study.
- Patients who have new medical problems develop during the study not thought to be related to study drug will be treated per standard of care medicine. If it is felt that the new condition makes it unsafe for the patient to continue in the study, then they will be withdrawn.
- Withdrawn patients will continue to be followed according to the schedule of the protocol and return for all assessment visits as tolerated and safe.

If patients have a history of diabetes the NIH endocrinology and/or blood glucose management team will be consulted for their ongoing care and to follow them during their treatment phase. If the blood sugar reaches a level that either of these teams feels warrants pausing treatment, treatment will be paused. Similarly, if CTCAE criteria are reached of level 3 or greater for hyperglycemia treatment will be paused. If blood sugar is reported as a value greater than 600 further doses will not be given until the consult team specifically reviews that result.

If patients have a history of anemia or develop anemia during the study hematology consult service will be consulted. If the consult service feels the patient's treatment should be paused it will be paused. If the patient's HgB value goes below 9 treatment will be paused until specific additional input from that value can be given by the hematology consult service.

### **14.3. Adverse Event Monitoring**

At each study contact, participants and/or their parents will be asked about any adverse events they have experienced. Any adverse events reported will be coded based on the Common Terminology Criteria for Adverse Events and logged.

The clinical site investigator will determine which events are associated with the use of study drug. For reporting purposes, an AE should be regarded as possibly related to the use of the investigational product if the investigator believes:

- There is a clinically plausible time sequence between onset of the AE and sodium thiosulfate administration; and/or
- There is a biologically plausible mechanism for sodium thiosulfate causing or contributing to the AE; and
- The AE cannot be attributed solely to concurrent/underlying illness, other drugs, or procedures.

An AE is deemed associated with the use of the study drug "if there is a reasonable possibility that the AE may have been caused by the drug" (21 CFR 312.32)

Known side effects of sodium thiosulfate include osteoporosis, hypotension, nausea, prolonged bleeding time, and metabolic acidosis. The development of kidney stones is a theoretical risk with the use of this medication. During treatment with sodium thiosulfate, we will perform specific targeted monitoring for these side effects as follows:

**Abbreviated Title:** Sodium Thiosulfate (STIC)

**Version Date:** July 07, 2023

- Osteoporosis will be monitored by DEXA scan at week 0, 6, 10, 24, and 62 for changes in bone mineral density. Height will also be measured for loss of stature.
- Blood pressure will be monitored before and after infusions to evaluate for alterations of blood pressure. It will be monitored every 30 minutes during the infusion and if the patient develops any symptoms.
- Nausea will be evaluated by patient reports.
- Prolonged bleeding time will be monitored by weekly laboratory evaluation of prothrombin time (PT) and partial thromboplastin time (PTT) from weeks 0 to 10 during the infusions.
- Metabolic acidosis will be evaluated by electrolyte and venous blood gas monitoring once per week from weeks 0 to 10 during the infusions. This has been attributed to mild metabolic acidosis immediately following infusion that potentially after several infusions without chance for the participant to equilibrate their acid base balance to baseline, could reach more clinically significant levels. This complication will be monitored more frequently in the initial 2 patients to ensure this remains true in our study population.
- Renal ultrasound will be used to monitor for the development of renal stones (when no CT scan is available), with assessments at weeks 6, 24, and 62.

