**Table 5 Type of Blood Test Performed or Sample Collected by Study Week in order of priority – Adult Subjects**

Blood Test/Sample	Collection Tube	Required Volume	Week Collected									
			Screening *	-10	0	1-5	6	7-9	10	24	62	
Acute care chemistry panel, mineral panel, hepatic panel, CK, LDH, total protein, Quantitative Immunoglobulins, C-Reactive Protein-High sensitivity, Pro Brain Natriuretic Peptide, CK-MB Immunoassay, uric acid, cystatin C, Thyroid screen (TSH, FT 4 )	Green/yellow Lithium Heparin Tube	One 4.0 mL tube	X	X	X	X d	X d	X d	X d	X	X	
Iothalamate (optional at week 24 and 62 if previously normal)	Heparinized Tube	Six 3 mL tubes		X e	X e			X e		X e	X b,e	X b,e
Venous Blood Gas, Ionized Magnesium Whole Blood, Ionized Calcium Whole Blood	Marquest Gaslyte Sampler	3 mL	X		X	X d	X d	X d	X d			
Aldolase	Red/yellow SST	One 4.0 mL tube	X	X	X			X		X	X	X
ANA, ENA, JO-1	Red/yellow SST	4 mL		X								
Complete blood count and differential	Light lavender top	One 3 mL tube	X	X	X			X		X	X	X
Erythrocyte Sedimentation Rate (ESR)	Black top	One 1 mL tube	X	X	X			X		X	X	X
Vitamin D, 25-Hydroxy, Vitamin D, 1,25-Dihydroxy	Red/yellow SST	One 4 mL tube		X	X			X		X	X	X

**Abbreviated Title:** Sodium Thiosulfate (STIC)

**Version Date:** July 07, 2023

Blood Test/Sample	Collection Tube	Required Volume	Week Collected								
			Screening *	-10	0	1-5	6	7-9	10	24	62
Parathyroid Hormone	Light Lavender	3 mL		X	X		X		X	X	X
IgE	Red/Yellow SST	4 mL		X	X	X d	X d	X d	X d	X	X
Bone Alkaline Phosphatase, Serum	Red-Yellow SST	0.6 mL		X	X		X		X	X	X
Thrombomodulin	Light Blue	4.5 mL		X	X		X		X	X	X
Hepatitis, HIV, HTLV-I serologies	Red/Yellow SST	8 mL	X	X	X						
PT,PTT, vWF panel, Factor VIII Activity	Blue-black	3 mL	X	X	X	X c	X	X c	X	X	X
HLA typing	Yellow ACD-A	Two 8.5 mL tubes		X							
Myositis autoantibody testing	Red/yellow SST	6 mL		X							
CHI RNA gene expression analysis	PAXgene Blood RNA	One 2.5 mL tube		X	X	X a	X		X	X	X
Endothelial activation markers	Blue-black	10-20 mL		X	X		X		X	X	X
CHI proteomics/ Cytokine Analysis	Red/yellow top (Greiner Vacutette serum tube with gel)	One 8 ml tube		X	X	X a	X		X	X	X

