**Table 8 Targeted Safety Monitoring Assessments**

	Inpatient Period - STS Infusions Given 3x Weekly			Follow-up Visits	
	Week 0	Week 6	Week 10	Week 24	Week 62
DEXA for osteoporosis	X a	X	X	X	X
Blood Pressure	X – taken before and after each infusion from Week 0 to Week 10				
Nausea	X – evaluated continually by patient report from Week 0 to Week 10				
PT/PTT	X – performed once per week from Week 0 to Week 10				
Renal Ultrasound		X		X	X
Electrolytes, venous blood gas	X – performed once per week from Week 0 to Week 10				

a. If a DEXA scan has been performed within 6 months prior to initiation of the study, that will be used as the baseline DEXA evaluation

*Abbreviated Title:* Sodium Thiosulfate (STIC)

*Version Date:* July 07, 2023

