## **Appendix G. Script for Assessing Adverse Events for Weeks 10-24**

For adult participants, the following questions will be asked. If the answer is an affirmative additional information will be asked for to obtain more details including the timing of any events, severity, and the associated outcomes.:

Since you were last at the NIH have you had to go to the hospital for any reason and if so why?

Since you were last at the NIH have you had any fractures or broken bones?

Since you were last at the NIH have you had any nausea or lightheadedness?

Since you were last at the NIH have you developed any pain when you urinate?

Since you were last at the NIH have you had any headaches?

Since you were last at the NIH have you experienced any episodes of disorientation or confusion?

Since you were last at the NIH have you had any episodes where you had difficulty stopping bleeding?

**FOR FEMALE PARTCIPANTS ONLY:** Since you were last at the NIH have you become pregnant?

**FOR MALE PARTICIPANTS, ONLY:** Since you were last at the NIH have any of your sexual partners become pregnant?

Since you were last at the NIH have you developed or been diagnosed with any new medical problems?

Since you were last at the NIH have you had any surgeries?

Have there been any changes in your medical condition that we have not asked about that you believe we should know about and if so what are they?

Since you were last at the NIH have you had any side effects from the sodium thiosulfate ?

Is there anything else you think we should be aware of for the study in terms of your health?

For pediatric participants, the following questions will be asked. If the answer is an affirmative additional information will be asked for to obtain more details including the timing of any events, severity, and the associated outcomes.:

Since your child was last seen at the NIH has he or she had to go to the hospital for any reason and if so why?

Since your child was last seen at the NIH has he or she had any fractures or broken bones?

Since your child was last seen at the NIH has he or she had any nausea or lightheadedness?

Since your child was last seen at the NIH has he or she developed any pain when you urinate?

Since your child was last seen at the NIH has he or she had any headaches?

Since your child was last seen at the NIH has he or she experienced any episodes of disorientation or confusion?

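### PT and PTT are named as the monitoring for prolonged bleeding time, but they do not measure it and no scheduled test does

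*Combined protocol and SAP*

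**What the plan says.** Section 14.3 states: "Known side effects of sodium thiosulfate include osteoporosis, hypotension, nausea, prolonged bleeding time, and metabolic acidosis". It promises specific monitoring for each effect and, for this one, says: "Prolonged bleeding time will be monitored by weekly laboratory evaluation of prothrombin time (PT) and partial thromboplastin time (PTT". Table 8 carries a PT/PTT row marked "performed once per week from Week 0 to Week 10" and has no row for bleeding time or platelet function.

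Other parts of the plan bear on bleeding:

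- Section 14.3 also says: "At each study contact, participants and/or their parents will be asked about any adverse events they have experienced". Table 4 schedules a formal adverse-event review at Weeks -10, -4 and 0, at every week from 1 to 10, and at Weeks 24 and 62.
- Tables 5 and 6 have a row "PT,PTT, vWF panel, Factor VIII Activity". Note c limits the draws in Weeks 1-5 and 7-9 to PT and PTT. The other marks, including Weeks -10, 0, 6 and 10, are unrestricted.
- The row "Complete blood count and differential" is marked at screening and at Weeks -10, 0, 6, 10, 24 and 62.
- Appendix G asks adults: "Since you were last at the NIH have you had any episodes where you had difficulty stopping bleeding". A matching question is put for children. Section 3.1 places these contacts between Weeks 11 and 13 and between Weeks 17 and 19.
- Section 8.1 plans McNemar tests for the incidence of adverse events.

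The side-effect lists in Sections 1.3 and 10.1.2.1 do not mention prolonged bleeding time.

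**The concern.** PT and PTT respond to clotting factors in plasma. Bleeding time depends on platelets, von Willebrand factor and the vessel wall. A drug could prolong bleeding time and leave both tests normal, so the named test does not observe the named effect.

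Safety of 10-week use is a secondary objective (Section 2), and adverse events, including laboratory abnormalities, are a secondary outcome (Section 2.1). Section 10.1.2.1 says that earlier safety data were not collected by consistent methods and points to Section 14.3 for targeted monitoring. A run of normal PT/PTT values, filed under bleeding time, could be read as evidence that bleeding time did not change. The treatment weeks are also when patients may have lines placed (Section 10.1.2.1), frequent blood draws (Tables 5 and 6) and small lesion aspirations (Section 5.16), so reassurance on this point would carry weight.

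**Working it through.** The plan gives no figure for bleeding, so the check is mainly a comparison of passages.

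**Step 1. Effect against measure, Section 14.3.**

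| Effect | Monitoring named | Observes the effect? |
|---|---|---|
| Osteoporosis | DEXA, height | Yes |
| Hypotension | Blood pressure around and during infusions | Yes |
| Nausea | Patient report | Yes |
| Metabolic acidosis | Electrolytes, venous blood gas | Yes |
| Kidney stones (theoretical) | Renal ultrasound or CT | Yes |
| Prolonged bleeding time | PT and PTT | No |

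Bleeding time is the only mismatch.

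**Step 2. What else could show it during Weeks 0-10.** The von Willebrand panel and Factor VIII are drawn at Weeks 0, 6 and 10, with a pre-treatment value at Week -10, but they address only part of what determines bleeding time. The blood count at Weeks 0, 6 and 10 counts platelets and does not test their function. Tables 5 and 6 contain no bleeding-time or platelet-function test at any week.

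**Step 3. Coverage of the scripted question.** It is used at two contacts, both after Week 10, and its recall window opens when the patient was last at the NIH. It therefore covers 0 of the 10 treatment weeks and 0 of the 10 pre-treatment weeks.

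**Step 4. Chance that overt bleeding is recorded anyway.** Section 8.3 gives 13 completers, 25% dropout and 18 enrolled; 13 / (1 - 0.25) = 17.3, rounded up to 18, reproduces the enrolment. The documents give no bleeding rate, so p is assumed at 5%, 10% and 20% per patient, with patients independent and every bleed reported. The chance of at least one report is 1 - (1 - p)^n:

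| p | n = 13 | n = 18 |
|---|---|---|
| 5% | 1 - 0.95^13 = 0.49 | 1 - 0.95^18 = 0.60 |
| 10% | 1 - 0.90^13 = 0.75 | 1 - 0.90^18 = 0.85 |
| 20% | 1 - 0.80^13 = 0.95 | 1 - 0.80^18 = 0.98 |

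If no patient reports bleeding, the one-sided 95% upper bound on the rate is 1 - 0.05^(1/n): 15% for n = 18 and 21% for n = 13. Both results depend on full reporting. General questioning without a bleeding prompt may fall short of that.

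**Step 5. The planned comparison.** Section 2.1 compares secondary outcomes between Week -10 to 0 and Week 0 to 10, and a McNemar test needs each patient's status in both periods. The pre-treatment interval is covered by two reviews (Weeks -4 and 0) and the treatment interval by ten (Weeks 1 to 10). Neither has a specified bleeding question.

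**The case against.** The strongest reply is that PT/PTT is not the trial's only route to a bleeding signal. Adverse events are asked about at every contact and coded by standard criteria. Inpatients are monitored daily and local outpatients three times weekly (Section 14.2). Review of systems and physical examination recur through treatment (Table 4). The von Willebrand panel and Factor VIII are already planned before and during treatment. Staff who place lines and draw blood would also see abnormal bleeding. All of this stands. A reader might infer that the trial would report no bleeding effect whether or not there is one. The documents do not support that: overt bleeding could be recorded, as Step 4 shows, and an effect on clotting factors could appear in PT/PTT.

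A reader might also infer that the number of PT/PTT draws measures the harm, or that a weekly von Willebrand panel would close the gap. Neither follows. Counting draws says nothing about missed events, and the panel reflects only one contributor to bleeding time.

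It can also be said that bleeding time is loose wording for clotting times, that Section 8.1 plans no bleeding-time endpoint, and that the misuse of PT/PTT is only a possibility. The first may be true, and the omission of the effect from Sections 1.3 and 10.1.2.1 leaves it open. But then the wording in Section 14.3 is wrong rather than the test, and the passage still has to change. The other two limit the consequence and do not remove the mismatch.

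**Conclusion.** Wrong as written. Section 14.3 and Table 8 assign to prolonged bleeding time a pair of tests that do not measure it, and no scheduled test does. A subclinical prolongation would go undetected, and normal PT/PTT cannot support a statement that bleeding time was unaffected. Overt bleeding during treatment can be captured, but only through general adverse-event questioning, because the scripted question starts after infusions end.

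The size of a missed silent effect cannot be stated, since nothing measures it. For overt bleeding, the chance of at least one report in 18 patients is 0.60 to 0.98 at assumed rates of 5% to 20% with complete reporting; even with no reports, a rate up to 15% could not be excluded. The mismatch itself rests on general laboratory knowledge of what PT and PTT measure, which the documents do not discuss. The primary endpoint is not affected.

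**What to change.** 1. In Section 14.3 and Table 8, describe PT and PTT as coagulation tests and report them as such, not as evidence on bleeding time. Cost: a wording change.

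2. Ask the existing Appendix G question on difficulty stopping bleeding at the adverse-event reviews that Table 4 already schedules from Week -10 through Week 10, and use the answers for the pre-treatment versus treatment comparison of bleeding. Reword the recall window to run from the previous review: during treatment the patient is an inpatient or attends three times weekly, so a window starting at the last time at the NIH would be days long or have no meaning. The reworded window also covers rapid responders, who skip the Week 7-9 assessments. Cost: one extra question per review, with no new visit, blood or instrument. Prompted reports may raise the count of minor events in both periods. With ten reviews on treatment against two before it, prompting will still be denser on treatment, and the report should say so.

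3. Reconcile the side-effect lists in Sections 1.3 and 10.1.2.1, which omit prolonged bleeding time, with Section 14.3, which calls it known, and state which effect PT/PTT is meant to track. Cost: an editorial amendment.
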